### **2.6      Analysis of secondary efficacy objective(s)**

#### **2.6.1      Secondary endpoints**

The following secondary efficacy variables were analyzed in an explorative manner:

- Occurrence of treatment failure up to Month 18 defined as composite endpoint of biopsy proven acute rejection of ISHLT 1990 grade  $\geq 3A$  resp. ISHLT 2004 grade  $\geq 2R$ , acute rejection episodes associated with hemodynamic compromise, graft loss / re-transplant, death, loss to follow up (at least one condition must be present).
- Occurrence of MACE and each of its components at Month 18

In addition to the analysis of the primary outcome variable of renal safety and tolerability, the following was analyzed:

- Renal function as assessed by Cockcroft-Gault at month 12 and 18 after Tx
- Serum creatinine and reciprocal creatinine slope (1/serum creatinine versus time) including the treatment period between BL (Month 6) and Month 18

#### **2.6.2      Statistical hypothesis, model, and method of analysis**

Event data:

Event rates were estimated using the Kaplan-Meier method to handle patients who discontinue the treatment prior to suffering from an event adequately. Time to event was defined as the time from date of randomization to the first documented date of the event. The two groups were compared using the log-rank test.

This procedure was applied for the composite endpoint of treatment failure and each of its components, as well as MACE and each of its components.

Narratives including relevant medical information were provided for each biopsy proven acute rejection, graft loss, or death.

Tolerability:

Analyses of renal function as determined by other calculations (serum creatinine, glomerular filtration rate (GFR, Cockcroft-Gault)) were evaluated in the same manner as described for the primary outcome measure.

The creatinine slope (1 / serum creatinine versus time) was determined from all assessments between Month 6 and Month 18 (both visits included) using a linear regression model. These slopes were compared with a two-sided Wilcoxon ranksum test between the treatment groups.

Additionally, tolerability of study medication was assessed from the rate of patients who withdraw prematurely from study medication or in whom study medication had to be converted to another immunosuppressive regimen due to abnormal laboratory results, adverse events, or toxicity. The frequency distribution of these reasons was presented with absolute and percent values. The most frequent reasons (total  $n \geq 5$ ) for discontinuation and/or conversion as well as the total number of patients who are affected by such intolerance of study medication were compared between the two treatment groups using the exact Fisher test.

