All patients who prematurely discontinue study treatment should still attend the final visit at Month 18 post transplantation to obtain follow up information on rejection episodes, allograft and patient survival, hospitalizations, malignancies and immunosuppressive medication.

The CRFs Study Completion Page should be completed at month 18 or earlier if the patient can no longer be followed, e.g. due to death, withdrawal of consent, or loss to follow-up.

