## 2 Statistical methods

### 2.1 Data analysis general information

All statistical analyses were performed [REDACTED]

[REDACTED] Analysis was carried out using the SAS (Statistial Analysis System) software, version 9.2, 2009, SAS Institute Inc., Cary, North Carolina, USA.

Analyses were done when all patients had completed the trial at 18 months post Tx (or discontinued prematurely).

The following periods were considered for analyses:

- The primary analysis of renal safety and tolerability concerns the **period of randomized treatment** between Month 6 (baseline) and Month 18 or the last assessment within this period in the event of a patient's premature discontinuation from the study. If indicated, e.g. for analysis of renal function and type and frequency of adverse events, the period from Month 6 to Month 18 was portioned into (a) the **switch period** between Month 6 and Month 9 and (b) the **maintenance period** between Months 9 and 18 after Tx.
- As a separate study period, the initial 3 months period between Screening and Baseline visit (**run-in period**) was analyzed with regard to treatment, efficacy, and safety of the immunosuppressive regimen.

In patients who discontinued prematurely from the study, the last available information under study treatmentwas analyzed.

Adverse events were analyzed separately for the initial 3 months period between Screening and Baseline visit (**Run-in period**) and for the randomized treatment period between Baseline visit (Month 6) and Month 18.

Significant events like rejection episodes, hemodynamic compromise, and MACE were additionally analyzed for the period between transplantation and Screening (Month 3 post Tx) (**Pre-screening period**).

Unless otherwise stated, all statistical tests were two-sided and used the 0.05 level of statistical significance. All summary statistics were presented by treatment group. Frequency distributions were provided for categorical variables. Descriptive statistics of mean, standard deviation, minimum, median and maximum were presented for continuous variables. Time to event data including rates of affected patients were assessed by Kaplan-Meier statistics and compared between the two groups with the logrank test.

Data from all centers that participated in this study were combined and the factor center was included in the analysis of the primary endpoint.

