### **2.6.3 Handling of missing values/censoring/discontinuations**

Missing values were imputed with the last observation carried forward (LOCF) method described at section 2.5.3.

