## 5 Appendix

### 5.1 Definitions

#### 5.1.1 Study periods

The following study periods were used for analysis:

- Pre-screening period: Tx – V1/M3/Screening
- Run-in period: V1/M3/Screening – V2/M6/Baseline
- Randomized treatment period: V2/M6/Baseline – V7/M18/EOS
  - Switch period: V2/M6/Baseline – V4/M9
  - Maintenance period: V4/M9 – V7/M18/EOS

In the event of a patient's premature discontinuation, the respective period was defined till the last assessment within this period.

For patients who discontinue prematurely from the study, both, the last available information under study treatment was analyzed.

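### The SAP sets no censoring rule for the event endpoints, and its wording on event follow-up after treatment stop conflicts with its own endpoint definition and with the protocol

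*SAP*

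**What the plan says.** The SAP has two sets of statements that bear on events after a patient stops treatment.

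**Pointing to on-treatment follow-up only**
- SAP 2.6.2 chooses Kaplan-Meier "to handle patients who discontinue the treatment prior to suffering from an event adequately". The reason named is leaving treatment; leaving follow-up is not mentioned.
- SAP 2.1, a general section, says that for patients who discontinued prematurely "the last available information under study treatmentwas analyzed". SAP 5.1.1 repeats this as "both, the last available information under study treatment was analyzed", where the second element announced by the first word is missing. Neither section exempts the event endpoints.

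**Pointing to follow-up through Month 18**
- SAP 2.6.1: "Occurrence of treatment failure up to Month 18 defined as composite endpoint".
- SAP 2.6.2: "Time to event was defined as the time from date of randomization to the first documented date of the event".
- SAP 5.1.1, for discontinuers: "the respective period was defined till the last assessment within this period". That is the last assessment, not the last dose.
- SAP 5.1.3 takes death from the Study completion CRF, which Protocol 6.5.6 has filled in at Month 18 or when the patient can no longer be followed.

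SAP 2.6.3, whose title includes censoring, says only: "Missing values were imputed with the last observation carried forward (LOCF) method described at section 2.5.3".

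Protocol 6.5.6 brings patients who stop treatment back at Month 18 "to obtain follow up information on rejection episodes, allograft and patient survival". Protocol 10.1 planned to analyse both the on-treatment information and the Month 18 assessment of discontinuers, and 10.5.4 planned an exploratory Month 18 analysis covering renal function and efficacy variables. SAP 2.12 reports no additional exploratory analyses, and SAP section 4 does not list the removal.

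**The concern.** Kaplan-Meier handles an event-free patient by censoring, so the censoring date decides which events count. The SAP does not give one. Two programmers could follow it faithfully and produce different curves, and the only explicit sentences about discontinuers lead to the narrower one.

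On that narrower reading, rejections, graft losses and deaths after stopping would be left out, although the protocol arranges to collect them. The censoring would probably be informative. Protocol 6.5.6 requires or permits withdrawal from treatment for rejection, adverse events, abnormal laboratory values and unsatisfactory effect, and under Protocol 7.1 later immunosuppression is at the investigator's discretion.

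The trial aims to show better renal function while expecting comparable efficacy (Protocol synopsis and section 2). Treatment failure and its components are the evidence for the second half of that statement.

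**Working it through.** **1. What each passage implies for an event after treatment stop**

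| Source | Event after stop, before Month 18 |
|---|---|
| SAP 2.1 and 5.1.1, information under study treatment | Not used |
| SAP 2.6.2, reason given for Kaplan-Meier | Points to censoring at stop |
| SAP 2.6.1, endpoint window | Counts |
| SAP 2.6.2, time-to-event definition | Counts |
| SAP 5.1.1, period ends at last assessment | Counts, if assessed |
| SAP 5.1.3, death from Study completion CRF | In the named source |
| SAP 2.6.3 | Silent; LOCF does not define a censoring time |
| Protocol 10.1 and 10.5.4 | Month 18 assessment is analysed too |

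SAP 2.1.1 defines a last contact, which would be a natural censoring date, but no endpoint rule uses it. Loss to follow-up is itself an event, dated in SAP 5.1.3 at the last known intake of study drug.

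**2. Size, if patients were censored at stop**

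The documents give no event rate, stopping rate or post-stop hazard for these endpoints, so there is no plan figure to reproduce. The sample size in Protocol 10.8 concerns GFR only. What follows is an illustration on assumed values.

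Set-up: 12-month window taken as 1, exponential times, on-treatment hazard λ, stopping hazard θ, hazard kλ after stopping, and 162/2 = 81 patients per arm (162 randomized, SAP 1.1).

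- First events before stop: λ/(λ+θ) × (1 − e^−(λ+θ))
- First events after stop: ∫₀¹ θ e^−(λ+θ)t (1 − e^−kλ(1−t)) dt
- Kaplan-Meier censored at stop estimates 1 − e^−λ

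Example with 10% on-treatment risk and 20% stopping: λ = −ln 0.90 = 0.1054, θ = −ln 0.80 = 0.2231. Before stop: 0.0898.

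| k | After stop | True risk | Kaplan-Meier censored at stop | Share of first events uncounted | Per 81 patients |
|---|---|---|---|---|---|
| 1 | 0.0102 | 10.0% | 10.0% | 10.2% | 0.83 |
| 2 | 0.0197 | 10.9% | 10.0% | 18.0% | 1.59 |
| 3 | 0.0285 | 11.8% | 10.0% | 24.1% | 2.31 |

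Over on-treatment risks of 5% to 20%, stopping of 10% to 30% and k from 1 to 3, the uncounted share runs from about 5% to 35%, or 0.2 to 6.5 first events per arm. With k = 1 the estimate is not biased, only less precise.

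**3. Effect on the contrast**

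Assumed monthly event hazards are 0.015 (CNI-free) and 0.0085 (CNI). Assumed stopping hazards are 0.03 and 0.015, that is about 30% and 16% stopping by 12 months. Censored Kaplan-Meier would show 1 − e^−0.18 = 16.5% and 1 − e^−0.102 = 9.7%, a difference of 6.8 points in every row below.

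| k, CNI-free | k, CNI | True CNI-free | True CNI | True difference (points) | Shown (points) |
|---|---|---|---|---|---|
| 3 | 2 | 20.7% | 10.5% | 10.3 | 6.8 |
| 1 | 1 | 16.5% | 9.7% | 6.8 | 6.8 |
| 0.5 | 2 | 15.2% | 10.5% | 4.8 | 6.8 |

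Differences are taken before rounding. The contrast can be understated, unchanged or overstated, depending on hazards that the documents do not give.

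**The case against.** The strongest reply is that no sentence in the SAP censors at treatment stop.

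- **Leaving the study is not stopping the drug.** SAP 2.1 speaks of discontinuing from the study, and Protocol 6.5.5 treats a patient who stops drug as withdrawn from the study only after the Month 18 assessments, or once it is clear that the patient will not return. This does not rescue the text: Protocol 10.1 and 10.5.4 use the same kind of phrase for patients who still have a Month 18 assessment, which is the half the SAP dropped.
- **The Kaplan-Meier sentence is inherited.** It comes almost unchanged from Protocol 10.6.1, where it stood beside a plan to use Month 18 data as well. This stands as a limit: the sentence alone does not prove censoring at stop.
- **The SAP is not a general on-treatment plan.** SAP 2.5.4 sets up LOCF-2 as a separate on-treatment method. That is fair, but it concerns GFR.
- **Deaths are in the data.** SAP 2.7.2 separates treatment deaths in the safety set from endpoint deaths in the FAS, and the Study completion CRF would hold a death after stopping. For rejection, Protocol 7.5 plans a biopsy at Visit 7.1. This stands.
- **The composite is partly protected.** A patient withdrawn for a qualifying rejection has already had a composite event, and loss to follow-up counts as one. This stands for the composite. It does not protect the separate death and graft-loss curves.

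A reader might infer that the SAP definitely loses rejections and deaths after stopping, or that this hides an efficacy cost of CNI withdrawal. The documents support neither. Censoring at stop is an inference with text against it, and the direction of any bias in the contrast is unknown.

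**Conclusion.** The point holds as a conflict and an omission. The SAP gives no censoring date for its event endpoints, its statements on discontinuers contradict its endpoint definition, and it drops the Month 18 analysis planned in Protocol 10.1 and 10.5.4 without declaring the change in section 4.

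If the on-treatment reading were programmed, about 5% to 35% of first events would go uncounted under the assumed ranges. Bias would arise only if the hazard changes after stopping. Its size and its direction in the treatment contrast cannot be derived from the documents.

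The consequence is bounded because SAP 2.6.1 labels these endpoints exploratory and the primary GFR analysis is not involved. The correction is still worth making: it could change the treatment-failure and component curves, and it relies on data already planned.

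**What to change.** - In SAP 2.6.2 and 2.6.3, state that all events from randomization to Month 18 count regardless of treatment discontinuation, and that event-free patients are censored at last contact (as defined in SAP 2.1.1) or Month 18.
- In SAP 2.1 and 5.1.1, exempt event endpoints from the wording on information under study treatment, and repair the incomplete sentence in 5.1.1.
- Limit the LOCF statement in 2.6.3 to the continuous renal variables.
- Show Kaplan-Meier with on-treatment censoring as a supportive analysis.
- Restore the protocol's Month 18 analysis of discontinuers, or declare and explain its removal in SAP section 4.
- Add a caveat for MACE. Protocol 7.1 continues routine MACE documentation for only 30 days after the last dose of the per-protocol regimen, so later non-fatal MACE rests on SAE reporting, which runs until 30 days after study participation ends.

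The cost is SAP wording and one supportive run. No new data are needed, because Protocol 6.5.5 and 6.5.6 already plan the Month 18 assessments for patients who stop treatment.

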### **2.6.3 Handling of missing values/censoring/discontinuations**

Missing values were imputed with the last observation carried forward (LOCF) method described at section 2.5.3.

## **2.7 Safety analyses**

### **2.7.1 Adverse events (AEs)**

Safety variables were analyzed separately

- for the period between Screening and Baseline (run-in period)
- for the period between Baseline and Month 9 (switch period)
- for the period between Month 9 and Month 18 (maintenance period)
- for the period between Baseline and final assessment (Month 18 or date of premature withdrawal from the study) (randomized treatment period),.

For the randomized treatment period, analyses of treatment emergent adverse events were performed according to the treatment group into which the patients were randomized.

All analyses of safety parameters were based on the safety population. For the period between Screening and Baseline visit summaries of all adverse events were displayed for the ENR population by randomization status, i.e. randomized versus not randomized patients.

The key safety variables which were analyzed are as follows.

- Incidence and severity of infections, in particular clinically apparent CMV
- Incidence and severity of Adverse Events (AEs) and Serious Adverse Events (SAEs)
- Incidence of AEs leading to discontinuation from the study
- Relative frequency of abnormal vital signs measurements and laboratory parameters

The incidence rates for (serious) adverse events and infections were analyzed by treatment group.

AEs/Infections:

Generally, infections data were analyzed together with AE data. In addition, infection data were analyzed separately.

Data collected by AE CRFs and by Infection CRFs and CMV-CRFs were coded with the MedDRA dictionary that gives preferred term and body system information. The incidence of AEs were summarized by body system, preferred term, severity, and relationship to study drug. All information pertaining to AEs noted during the study were listed by treatment group and patient, detailing verbatim given by the investigator, the preferred term, the body system, start/end dates, severity and drug relatedness. The AE onset was also shown relative (in number of days) to the day of initial dose per study period (within the first 3 months, after Baseline (Month 6)).

In addition to being analyzed similarly as AEs, as described above, the relative frequency of infection by type and micro-organism was tabulated. AEs occurring 30 or more days after the discontinuation of study medication were not included in AE/infection summary tables.

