7.2 Information to be collected on Screening failures

If a patient who signed informed consent fails to be **enrolled** into the trial at Month 3 for any reason, the patient's number and the reason for non-enrollment will be entered into the Screening Failure Log.

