10.6.2 Safety

Safety variables will be analyzed separately for the period between a) Screening and Baseline, b) for the period between Baseline and Month 9, c) for the period between Baseline and final assessment (Month 18 or date of premature withdrawal from the study), d) as well as for the total treatment period (Screening to Month 18). For the randomized treatment period, analyses will be performed according to the treatment group into which the patients were randomized.

All analyzes of safety parameters will be based on the safety population. Corresponding data from the NRP group will be described similarly for the period between Screening and Baseline visit.

The key safety variables which will be analyzed will be as follows.

- Incidence and severity of infections, in particular clinically apparent CMV
- Incidence and severity of Adverse Events (AEs) and Serious Adverse Events (SAEs)
- Incidence of AEs leading to discontinuation from the study
- Relative frequency of abnormal vital signs measurements and laboratory parameters

The incidence rates for (serious) adverse events and infections will be analyzed by treatment group.

AEs/Infections

Generally, infections data are analyzed together with AE data. In addition, infection data will be analyzed separately.

Data collected by AE CRFs and by Infection CRFs and CMV-CRFs are to be coded with the MedDRA dictionary that gives preferred term and body system information. The incidence of AEs will be summarized by body system, preferred term, severity, and relationship to study drug. All information pertaining to AEs noted during the study will be listed by treatment group and patient, detailing verbatim given by the investigator, the preferred term, the body system, start/end dates, severity and drug-relatedness. The AE onset will also be shown relative (in number of days) to the day of initial dose per study period (within the first 3 months, after Baseline (Month 6)).

In addition to being analyzed similarly as AEs, as described above, the relative frequency of infection by type and micro-organism will be tabulated. AEs occurring 7 or more days after the discontinuation of study medication will not be included in AE/infection summary tables.

Laboratory data

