## **2.2 Analysis sets**

The **Enrolled Patient Population (ENR)** includes all patients who signed an informed consent regardless whether they received study treatment or not.

The **Safety Population (SAF)** consists of all patients who signed an informed consent and who were treated with at least one dose of any immunosuppressive medication after the Screening visit. Note: The statement that a patient had no adverse events constitutes a safety assessment.

The **Randomized Population (RAN)** is defined by all patients who were randomized at Baseline visit. This population will also include patients who were randomized but not treated with the randomized medication.

The **Full Analysis Set (FAS)** consists of all randomized patients who received at least one dose of any immunosuppressive therapy after Baseline Visit (Month 6) and have at least one

post-baseline assessment of the primary outcome variable (renal function based on MDRD method). Randomized patients without data on the primary outcome variable will be excluded from this population; their data will be analyzed for the initial treatment period (up to Month 6) and within the RAN and SAF. Following the intent-to-treat principle, patients will be analyzed according to the treatment group they were assigned to at randomization.

The **Per-protocol Population (PP)** consists of all FAS patients who did not show major deviations from the protocol procedures that may have an impact on the study outcome and who have completed the treatment period at Month 18 according to protocol. Criteria that are assumed to have such an impact were defined before analysis during the Blind Review Meeting and are documented in the Appendix, section 5.6 Rule of exclusion criteria of analysis sets.

For the period before Baseline visit (Month 6) the enrolled patient population was divided by randomization status into randomized patients and not randomized patients.

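### The SAP moves the run-in adverse event tables from the safety population to all consented patients; this can dilute the not-randomized column, and unequal follow-up can lower it further under either set

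*SAP*

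**What the plan says.** Protocol 10.6.2 states that "All analyzes of safety parameters will be based on the safety population", with the data of the not-randomized group described in a similar way from Screening to Baseline. Protocol 10.2 defines that group as transplanted patients who did not qualify at Month 6.

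SAP 2.7.1 repeats the rule ("All analyses of safety parameters were based on the safety population"). Its next sentence then says that, for Screening to Baseline, "summaries of all adverse events were displayed for the ENR population by randomization status".

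SAP 2.2 defines the two sets:
- ENR "includes all patients who signed an informed consent regardless whether they received study treatment or not".
- SAF adds the condition of having been "treated with at least one dose of any immunosuppressive medication after the Screening visit".

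For the period before Baseline, SAP 2.2 also says that "the enrolled patient population was divided by randomization status into randomized patients and not randomized patients". It provides no third category for screening failures.

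For a patient who consents but fails at Month 3, Protocol 7.2 requires only that the patient's "number and the reason for non-enrollment will be entered into the Screening Failure Log".

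SAP section 4 records that not-randomized patients are considered for the run-in only. It does not mention the move from SAF to ENR.

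**The concern.** Two adjacent sentences in SAP 2.7.1 name different sets for the same tables. The second set, as defined, can include people for whom adverse events were hardly collected.

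Protocol 7.6 counts an adverse event only once study drug has started, and screening failures leave nothing but a log entry. Such a patient adds one to the denominator and, serious events aside, nothing to the numerator. Every such patient falls in the not-randomized column, because randomized patients by definition passed Screening.

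A second, separate matter affects the same column. Randomized patients were all followed to Month 6, whereas some of the others left before then. SAP 2.7.1 specifies incidence and gives no measure that allows for time observed.

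Under SAP section 4 these run-in tables are the only planned adverse event summaries for patients who did not reach randomization. Both effects push that column down, so the group that did not get through run-in could look safer than it was.

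**Working it through.** **Inputs.** SAP 1.1 gives 162 randomized patients. Neither document gives the number consented, failing Screening or leaving during run-in, nor any run-in incidence, so there is no plan figure to reproduce. The values of p, s and f below are assumptions.

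**Step 1: who is in which set.**

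| Patient | In ENR | In SAF | Non-serious AEs collected |
|---|---|---|---|
| Randomized | yes | yes | to Month 6 |
| Entered run-in, failed at the Month 6 check | yes | yes | to Month 6 |
| Entered run-in, left before Month 6 | yes | yes | until observation ends |
| Consented, failed Screening | yes, as defined | unclear | essentially none |

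The last SAF entry is unclear because the SAF condition is met by any immunosuppressive dose after Screening. A heart recipient three months after transplant can be expected to take one whether or not the trial accepts the patient.

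**Step 2: dilution.** Let p be the incidence among patients with event collection, and s the share of the not-randomized column without it. The displayed incidence is p × (1 − s).

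| p | s = 0 | s = 10% | s = 25% | s = 50% |
|---|---|---|---|---|
| 30% | 30% | 27% | 22.5% | 15% |
| 60% | 60% | 54% | 45% | 30% |
| 90% | 90% | 81% | 67.5% | 45% |

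The relative loss equals s whatever p is. In the randomized column s = 0.

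**Step 3: shorter observation.** Let p be the incidence over the full three months, and f the fraction of that time observed in a patient who leaves for a reason unrelated to an event. With a constant hazard the expected incidence is 1 − (1 − p)^f.

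| p | f = 1 | f = 0.75 | f = 0.50 | f = 0.25 |
|---|---|---|---|---|
| 30% | 30% | 23.5% | 16.3% | 8.5% |
| 60% | 60% | 49.7% | 36.8% | 20.5% |
| 90% | 90% | 82.2% | 68.4% | 43.8% |

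These figures are for a group in which everyone is observed for the same fraction f. A column that mixes such patients with others followed to Month 6 lies between f = 1 and the value shown. Early leavers were treated and so belong to both sets; replacing ENR by SAF leaves Step 3 unchanged.

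**Step 4: does a rate help?** Assume a hazard of 0.2 per month in both groups.
- Full three months: 1 − exp(−0.6) = 45.1%.
- Uniform exit over three months (mean 1.5 months), no observation afterwards: 1 − (1 − exp(−0.6))/0.6 = 24.8%.
- Patients with an event per 100 patient-months of observation: 45.1/3 = 15.0 and 24.8/1.5 = 16.5.

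The percentages are far apart although the hazards are identical; the rates nearly agree. A patient who never entered run-in contributes no patient-months, so the rate is also free of the dilution in Step 2.

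**The case against.** The strongest reply is that ENR was chosen on purpose. SAP 2.2 defines the ENR split for the period before Baseline, SAP 2.4.1 uses it for run-in duration and dose, and the ENR sentence in 2.7.1 can be read as a specific exception to a general rule. It may well be deliberate. But the sentence before it says all analyses, Protocol 10.6.2 says the same, and section 4 does not declare the exception.

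Several further points stand and limit the concern:
- Whether log-only patients are in the ENR dataset is not settled. The Protocol glossary ties enrollment to consent, while Protocol 6.3 and 7.2 describe screening failures as not enrolled.
- Serious events are reportable from consent (Protocol 8.1), so collection in these patients is minimal rather than nil.
- Patients who leave because of an adverse event already count as having one. Patients excluded at the Month 6 check have the whole run-in observed.
- The tables are descriptive, and no test between the two columns is specified.

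A reader might infer that incidence is definitely understated, and take the 45.1% against 24.8% in Step 4 as its size. The documents support neither. They give no hazard and no exit pattern, and that model makes exit independent of events and ends observation at exit. Protocol 6.5.5 and 7.1 provide for safety contact in the 30 days after stopping, and SAP 2.7.1 drops only events 30 or more days after stopping. Adding one month of observation, capped at Month 6, gives 1 − [(exp(−0.2) − exp(−0.6))/0.2 + exp(−0.6)]/3 = 36.7% instead of 24.8%. SAP 5.1.1, however, ends the period at the last assessment, so even the length of observation is not fixed.

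A reader might also infer that going back to SAF would cure the problem. It need not remove screening failures (Step 1), and it does nothing about early leavers (Step 3).

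**Conclusion.** The concern holds in a limited form. The SAP contradicts itself on the set for run-in adverse events and does not declare the departure from the protocol. If ENR is applied as defined, each consented patient who never entered run-in treatment lowers the crude incidence in the not-randomized column only, by a relative amount equal to the share of such patients. That share is not given and may be zero.

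Separately, early exit for reasons other than an adverse event can lower the same column under either set. This assumes that such exits occurred, and its size cannot be derived from the documents. Both effects run in the same direction.

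The matter is minor: it concerns the reading of a descriptive run-in table. The primary endpoint and the randomized comparison are untouched.

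**What to change.** 1. For the run-in adverse event and infection tables, define the denominator as patients who entered run-in and took at least one dose of the study regimen after Screening, split by randomization status.
2. Show screening failures in the disposition summary (SAP 2.3.1) only, and state whether log-only patients belong to ENR.
3. For each column, add patient-months from Screening to Month 6 or to the end of adverse event observation, and the number of patients with an event per 100 patient-months. State which date ends observation for patients who leave, since SAP 2.7.1 and 5.1.1 point to different ones.
4. Reconcile the two sentences in SAP 2.7.1 and list the change of set in SAP section 4.

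The cost is SAP wording and re-running the run-in tables; no new data are needed. The one drawback is that the run-in exposure tables in SAP 2.4.1 use ENR and should be moved to the same denominator, so that exposure and events can be read together.
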